6.7.3 MTD

Dose escalation will follow a modified 3+3 plan (Table 3) using the dose levels listed in Table 1 and the guidelines in Table 2 to determine the MTDs and the RP2Ds for AR-42 and pazopanib. DLT is defined in Section 6.7.2. Patients will be enrolled in cohorts of 3 beginning at dose level 1.

Table 3. Modified 3+3 Dose Escalation		
Number of Patients with DLT at a Given Dose Level (Refer to Section 6.7.2 for DLT definition)	Escalation Decision Rule (Refer to Table 1 in Section 6.6 for dose levels and Table 2 for dose-escalation guidelines)	
0 out of 3	Enroll 3 patients at the next dose level.	
≥ 2 ^A	MTD has been exceeded. No further treatment at this dose is allowed. Three (3) additional patients will be enrolled per dose levels as noted on Table 2 .	
1 out of 3 ^A	Enroll at least 3 more patients at this dose level.	
	 If 0 of these 3 patients experience DLT, escalate doses to the next dose level (unless MTD has already been exceeded at that dose level, in which case, the current dose level is the MTD).^B 	
	• If 1 or more of this group experience DLT (total of 2), then the MTD has been exceeded. Three (3) additional patients will be enrolled at the next lower dose level if only 3 patients were treated previously at that dose. ^B	
Patients enrolled to complete a total enrollment of 12 at the MTD		
≤ 3	The MTD has been confirmed. ^B	
≥ 4	The MTD has been exceeded; 3 additional patients will be enrolled at the next lower dose level (if available). ^B	
	3 PPE at any dose level will NOT be considered a DLT. grade 3 PPE will be considered DLT.)	
 B. Confirmation that a dose level does not exceed the MTD requires evaluation of a minimum of 6 DLT-evaluable patients. To confirm the RP2Ds, additional patients will be enrolled at the MTDs until a total of 12 patients have been treated at the MTDs. 		

 Table 3. Modified 3+3 Dose Escalation

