6.6 AR-42 and Pazopanib Dose-Escalation Plan

The dose-escalation plan is based on the available dose levels listed on Table 1, the dose level instructions outlined on Table 2, and the modified 3+3 design on Table 3.

- The initial cohort of patients will be assigned to an AR-42 dose of 20 mg taken once per day on 3 non-consecutive days during the first 3 weeks of each 4-week cycle and a pazopanib dose of 600 mg once daily continuously.
- The treatment schedule as described in Section 6.2 will remain the same for all dose levels.
- The initial escalation will only affect the pazopanib dose so that the FDA-approved full dose of pazopanib (800 mg) is provided early in the dose-escalation plan. In subsequent dose-escalation steps, the dose of AR-42 will be increased in 10-mg increments until the maximum AR-42 dose of 40 mg is reached.
- If the number of DLTs indicates that the MTD has been exceeded with a pazopanib dose of 800 mg, the pazopanib dose will be decreased to 600 mg and the AR-42 dose will continue to increase in 10-mg increments regardless of relationship of the DLT to one or both study medications.

-		600 mg	800 mg
	10 mg	-1	N/A
AR-42 Dose	20 mg	1 (Starting Dose Level)	2
Dose	30 mg	3B	3A
	40 mg	4B	4A

Table 1. AR-42 and Pazopanib Dose Levels

Pazopanib Dose

	AR-42 Dose (Taken orally)	Pazopanib Dose (Taken orally)	
Dose Level	Once per day on 3 non-consecutive days/week during the first 3 weeks of each 4-week cycle	Once per day continuously during each 4-week cycle	
-1	10 mg	600 mg	
 If 0 or 1 DLT is observed with Dose Level -1, the MTD will be Dose Level -1. If ≥ 2 DLTs are observed at Dose Level -1, the lowest possible dose level was not tolerated. 			
1 (Starting Dose Level)	20 mg	600 mg	
 If 0 or 1 DLT is observed with Dose Level 1, the next cohort will receive Dose Level 2. If ≥ 2 DLTs are observed at Dose Level 1, the next cohort will receive Dose Level -1. 			
2	20 mg	800 mg	
 If 0 or 1 DLT is observed with Dose Level 2, the next cohort will receive Dose Level 3A. If ≥ 2 DLTs are observed at Dose Level 2, the next cohort will receive Dose Level 3B. 			
3A	30 mg	800 mg	
3B	30 mg	600 mg	

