 If 0 or 1 DLT is observed with Dose Level 3A, the next cohort will receive Dose Level 4A. If ≥ 2 DLTs are observed at Dose Level 3A, the next cohort will receive Dose Level 3B. If 0 or 1 DLT is observed with Dose Level 3B, the next cohort will receive Dose Level 4B. If ≥ 2 DLTs are observed at Dose Level 3B, the highest dose level without ≥ 2 DLTs will be the MTD. 			
4A	40 mg	800 mg	
4B	40 mg	600 mg	
 If 0 or 1 DL 	T is observed with Dose Level 4/	A, the MTD will be Dose Level 4A.	
– If ≥ 2 DLTs	are observed at Dose Level 4A,	the next cohort will receive Dose Level 4B.	
 If 0 or 1 DLT is observed with Dose Level 4B, the MTD will be Dose Level 4B. If ≥ 2 DLTs are observed at Dose Level 4B, the MTD will be the highest dose level without ≥ 2 DLTs. 			

Table 2. AR-42 and Pazopanib Dose-Escalation Guidelines

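### After 2 DLTs in 6 at an 800-mg level, Table 3 sends the next patients back to a level already treated, while Table 2 sends them on to 3B or 4B, and nothing says which prevails

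*Combined protocol and SAP*

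**What the plan says.** Section 6.6 sets out a two-drug grid: AR-42 10 to 40 mg by pazopanib 600 or 800 mg. Levels 2, 3A and 4A carry 800 mg of pazopanib; levels 1, 3B and 4B carry 600 mg.

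- **Section 6.6 text**, once the MTD is exceeded at 800 mg: "the pazopanib dose will be decreased to 600 mg and the AR-42 dose will continue to increase in 10-mg increments".
- **Table 2, level 2**: "If ≥ 2 DLTs are observed at Dose Level 2, the next cohort will receive Dose Level 3B".
- **Table 2, level 3A**: "If ≥ 2 DLTs are observed at Dose Level 3A, the next cohort will receive Dose Level 3B". Failure at 4A leads to 4B in the same way.
- **Table 3, row for 2 or more DLTs** (no denominator given): "Three (3) additional patients will be enrolled per dose levels as noted on" Table 2.
- **Table 3, row for 1 DLT in 3, second bullet**: "If 1 or more of this group experience DLT (total of 2), then the MTD has been exceeded". The action is then "Three (3) additional patients will be enrolled at the next lower dose level if only 3 patients were treated previously at that dose".
- **Table 3, same row, first bullet** (1 in 3, then 0 in 3): escalate, "unless MTD has already been exceeded at that dose level, in which case, the current dose level is the MTD".

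Footnote B to Table 3 requires at least 6 DLT-evaluable patients to confirm a level.

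**The concern.** Two rules cover one event and name different levels. The second bullet is ordinary single-agent 3+3 wording in which the level below is simply the previous one. In this grid, Table 2's destination after a failure at 800 mg is a side step to a level that nobody has received. It cannot satisfy the bullet's condition that exactly 3 patients were treated there.

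Read row by row, Table 3 also orders the evidence backwards. Two DLTs in 3 at level 2, the stronger signal, moves patients to AR-42 30 mg with pazopanib 600 mg. Two in 6, the weaker signal, returns them to 20 mg with 600 mg.

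What is at stake is the dose of the next cohort and possibly the MTD. The MTD caps the RP2D, which is the primary endpoint, and determines which level is expanded to 12 patients.

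**Working it through.** **1. The plan's own figures (Section 13.2).** 6 levels × 6 patients = 36 evaluable; 36/0.8 = 45; 45 + 6 = 51. At 4.5 patients per cohort, 4 levels give 18 and 5 give 22.5, taken as 23; 18/0.8 and 23/0.8 round up to 23 and 29; adding 6 gives 29 and 35. All reproduce.

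**2. The two instructions side by side**, after 1 DLT in 3 and then at least 1 in 3, where the level below has had only 3 patients:

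| Failed level (AR-42/pazopanib, mg) | Table 3 bullet | Table 2 | AR-42 per cycle (9 doses) | Pazopanib per cycle (28 doses) |
|---|---|---|---|---|
| 2 (20/800) | 1 (20/600) | 3B (30/600) | 180 vs 270 mg | 16.8 g in both |
| 3A (30/800) | 2 (20/800) | 3B (30/600) | 180 vs 270 mg | 22.4 vs 16.8 g |
| 4A (40/800) | 3A (30/800) | 4B (40/600) | 270 vs 360 mg | 22.4 vs 16.8 g |

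For 3A and 4A one might loosely call 3B and 4B lower, since they have the same AR-42 and less pazopanib, but they do not meet the prior-treatment condition. For level 2 even that reading fails, because 3B has more AR-42. If the level below already has 6 patients, the bullet adds none and names no next cohort.

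**3. How usual the event is.** For a true DLT rate p, failure at once has probability A = 3p²(1−p) + p³. Failure by 1 in 3 and then at least 1 in 3 has probability h = 3p(1−p)²[1−(1−p)³]. The share by the second route is h/(A+h):
- p = 0.20: 0.187/(0.104+0.187) = 64%
- p = 0.30: 0.290/(0.216+0.290) = 57%
- p = 0.40: 0.339/(0.352+0.339) = 49%

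**4. How often the tables name different next cohorts.** The documents give no DLT rates, so these are assumptions, for levels 1, 2, 3A, 4A, 3B, 4B:
- mild: .05 .10 .15 .25 .10 .20
- middle: .10 .15 .25 .40 .20 .30
- steep: .10 .20 .35 .50 .25 .40

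Let a = (1−p)³ be the probability of 0 in 3, and f = a + 3p(1−p)⁵ the 3+3 pass probability. Counting only cases where the level below passed at 0 in 3, the probability is a(p1)h(p2) + f(p1)a(p2)h(p3A) + f(p1)f(p2)a(p3A)h(p4A):
- mild: .0565 + .0890 + .1321 = 27.8%
- middle: .0915 + .1357 + .1054 = 33.3%
- steep: .1366 + .1493 + .0579 = 34.4%

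**5. Only if the bullet is also taken to end escalation.** Let k be the probability of at most 1 DLT in the 3 added patients. Multiply the three terms by k(p1)f(p3B), k(p2)f(p3B) and k(p3A)f(p4B):
- mild: .0508 + .0784 + .0879 = 21.7%
- middle: .0630 + .0903 + .0439 = 19.7%
- steep: .0797 + .0802 + .0129 = 17.3% (terms rounded)

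This counts 0 in 3 at a top level as confirmed. Requiring 6 patients, as footnote B does, gives 20.8%, 18.2% and 15.7% by simulation.

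Four other assumed profiles, same level order, 100,000 simulated trials each with identical patient outcomes under both rules:
- toxicity driven by 800 mg pazopanib (.08 .33 .40 .50 .12 .18): 40%
- both drugs (.10 .20 .30 .42 .18 .28): 32%
- driven by AR-42 (.10 .13 .30 .50 .27 .45): 18%
- low toxicity (.05 .10 .15 .20 .10 .15): 29%

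These runs also stop at a lower level that already has 6 patients, so they count more divergent cases. None of the figures includes the 12-patient expansion rule.

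**6. One path.** Level 1 has 0 in 3, level 2 has 2 in 6, and no other DLT occurs. Table 2 ends at 4B (40/600) after 18 patients. The stopping reading ends at level 1 (20/600) after 12.

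**The case against.** The best defence is that the plan, read as a whole, follows Table 2. The Section 6.6 text says so. Table 3's row for 2 or more DLTs has no denominator, so it also covers 2 in 6 and hands over to Table 2. The lead sentence of Section 6.7.3 and the Table 3 column header both refer to Table 2. Section 13.2 expects 4–5 levels to be explored. Table 2's routes that reach a 40-mg level use 4 or 5, whereas stopping after a failure at level 2 or 3A would use 2 or 3. There is also a reading that keeps every sentence in use: follow Table 2 where it names a next cohort, and use the bullet only where Table 2 declares an MTD, for example when 4B fails with 2 in 6 after 3B passed at 0 in 3.

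All of that stands as evidence of intent. It does not remove the conflict, because the bullet gives its own destination and no sentence ranks the tables.

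A reader might go further and infer that Table 3 validly ends the search at level 1, 2 or 3A, so that two different MTDs would both comply with the protocol. The documents do not support that. The parenthesis that declares the current level the MTD is written for 1 in 3 followed by 0 in 3. Carrying it over to a level with 0 in 3 plus 3 more is an extrapolation, and stopping would contradict Section 6.6.

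Section 14.1 has the study team address the intervention for the next patient, which could catch the problem but supplies no rule.

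**Conclusion.** The second bullet of Table 3's row for 1 DLT in 3 is wrong for this grid and should be corrected. The certain consequence is a conflicting instruction on the next cohort's dose after a common type of failure at levels 2, 3A and 4A, when the level below has had only 3 patients. Under the assumed rates that arises in about 28–34% of trials. A different MTD is possible but conditional: it requires the team both to follow the bullet and to treat it as the end of escalation. On that condition the rate is roughly 16–22%, or 18–40% under the other profiles. All percentages rest on DLT rates that the documents do not give, and they show only that this is not a rare corner case. They are not a forecast that the trial will reach the wrong MTD.

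**What to change.** 1. Reword the second bullet: *If one or more of the second three patients have a DLT (two or more in total), the MTD has been exceeded and the next cohort is the level named in Table 2.*
2. Put the backfill where it is needed: *When Table 2 declares an MTD at a level with fewer than 6 DLT-evaluable patients, enrol to 6 there before expansion.*
3. Leave the first bullet's parenthesis as it is. If 4A fails in the 12-patient expansion and 3A then shows 1 in 3 and 0 in 3, the parenthesis is what prevents re-escalation to 4A.
4. Optional: where Table 2 says "the MTD will be the highest dose level without ≥ 2 DLTs", add that levels rank by level number, so that 3B rather than 2 is chosen when 3A and 4B have failed and both 3B and 2 are tolerated.

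The cost is a few words. Some paths use more patients than stopping early would (18 against 12 in the path above). The largest number in the simulations under Table 2 routing, with backfill to 6, was 36, which equals the maximum stated in Section 13.2.

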6.7 Definitions of Dose-Limiting Toxicity, Maximum Tolerated Dose, and Recommended Phase 2 Dose

6.7.1 DLT-Evaluable Criteria

The DLT evaluation period will be the first treatment cycle. Patients must have taken a minimum of 6 AR-42 doses **and** a minimum of 21 pazopanib doses during cycle 1 to be considered evaluable for DLT, if DLT has not been observed at the delivered dose.

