13 STATISTICAL CONSIDERATIONS

13.1 Study Design

This is a phase 1 study of AR-42 in combination with pazopanib in patients with advanced RCC or STS. A modified 3+3 dose-escalation design will be conducted. Additional patients will be enrolled at the MTD until a total of 12 patients have been treated at the MTD.

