13.2 Sample Size/Accrual Rates

With the 7 proposed dose levels (-1, 1, 2, 3A, 3B, 4A, and 4B) and starting at dose level 1 (as indicated in Table 1 in Section 6.6), the number of patients needed for evaluation of DLT ranges from 4 to 36. To take into account the up to 20% of patients subsequently found to be inevaluable for DLT, the maximum number of patients required to determine the MTD is 45. Per the dose-escalation plan, it is likely that 4-5 dose levels will be explored. With an average of 4.5 patients per cohort, the likely scenarios involve 18-23 patients and, therefore, it is expected that 23-29 patients evaluable for DLT will be enrolled in the study. With 6 additional patients who will be treated at the MTD, the maximum number of patients needed for the study is 51 with a likely sample size of 29-35 patients.

Based on past recruitments, the recruitment rate is expected to be about 1-2 per month. Therefore, the anticipated enrollment period is expected to be about 15-35 months.

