13.6 Evaluability for DLT, Toxicity, and Response

13.6.1 DLT-Evaluable Population

DLT-evaluable patients are those who have taken a minimum of 6 doses of AR-42 during the first treatment cycle and a minimum of 21 doses of pazopanib during the first treatment cycle, or those who have experienced a DLT with any study treatment during cycle 1 as described in Section 6.7.1.

Note: Patients who for any reason are not evaluable for DLT will be replaced.

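### The rule that confirms the MTD is tied to 12 treated patients and the sample size adds a flat 6, which conflicts with the rule replacing every DLT-inevaluable patient

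*Combined protocol and SAP*

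**What the plan says.** The number at the MTD is described in several places of the combined protocol and SAP, never as 12 evaluable patients.

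- Section 13.1: "Additional patients will be enrolled at the MTD until a total of 12 patients have been treated at the MTD". Section 3.1 also counts patients treated, and so does footnote B of Table 3: "additional patients will be enrolled at the MTDs until a total of 12 patients have been treated at the MTDs".
- In Table 3 (Section 6.7.3), the confirmation rows stand under the sub-header "Patients enrolled to complete a total enrollment of 12 at the MTD". With 3 or fewer DLTs, "The MTD has been confirmed"; with 4 or more it has been exceeded. The rows give no denominator.
- Footnote B uses the evaluable term only for a floor: confirming that a dose does not exceed the MTD "requires evaluation of a minimum of 6 DLT-evaluable patients".
- Section 6.7.1 defines evaluability for a patient without a DLT: "Patients must have taken a minimum of 6 AR-42 doses and a minimum of 21 pazopanib doses during cycle 1".
- Section 13.6.1: "Patients who for any reason are not evaluable for DLT will be replaced". It makes no exception for the expansion.
- Section 13.2 allows for up to 20% inevaluable patients when it moves from 36 to 45 for the escalation, and then: "With 6 additional patients who will be treated at the MTD, the maximum number of patients needed for the study is 51".

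**The concern.** The count of at most 3 against at least 4 DLTs is the last formal step before the MTD, and the MTD caps the RP2D, which is the primary endpoint. A patient without a DLT who takes too few cycle 1 doses is not evaluable. Such a patient can still fill one of 12 treated places, and cannot add a DLT. If the expansion stops at 12 treated patients, these patients work as if they had shown no DLT, and the rule leans toward confirming the dose.

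The treated wording and the flat 6 point to that reading; Section 13.6.1 points to the opposite one. No section says which governs the confirmation count.

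**Working it through.** **Reproducing the plan's sample size (Section 13.2)**

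- Escalation maximum: 36 / 0.8 = 45. Total: 45 + 6 = 51, as stated.
- Likely range: 4 to 5 levels × 4.5 patients = 18 to 22.5, taken as 18 to 23. Then 18 / 0.8 = 22.5, so 23, and 23 / 0.8 = 28.75, so 29. Adding 6 gives 29 to 35, as stated.

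The 20% allowance is therefore applied to the escalation only. The 6 expansion patients carry none.

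**Evaluable patients if the expansion stops at 12 treated**

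Footnote B already requires 6 evaluable patients, so only the 6 added patients are exposed to inevaluability. At the plan's upper rate of 20%:

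- Expected evaluable: 6 + 6 × 0.8 = 10.8.
- P(all 12 evaluable) = 0.8^6 = 0.262; P(11) = 6 × 0.2 × 0.8^5 = 0.393.
- P(10 or fewer) = 1 − 0.262 − 0.393 = 0.34 (unrounded 0.3446). P(10) = 0.246, so P(9 or fewer) = 0.10.

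**Chance of confirming the dose**

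The documents state no target DLT rate and no operating characteristics, so the true rates p below are assumptions. Inevaluability is taken as independent of DLT risk. There are two steps: at most 1 DLT in the first 6 evaluable patients, then at most 3 in total. With X the DLTs in the first 6 and Y those counted in the added 6:

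P(both steps) = P(X = 0) × P(Y ≤ 3) + P(X = 1) × P(Y ≤ 2)

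X is Binomial(6, p). Y is Binomial(6, p) if inevaluable patients are replaced, and Binomial(6, 0.8p) if they are not.

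At p = 0.40:

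- P(X = 0) = 0.0467 and P(X = 1) = 0.1866, so the first step is passed with probability 0.233.
- Replaced: 0.0467 × 0.8208 + 0.1866 × 0.5443 = 0.140; given the first step, 0.140 / 0.233 = 0.60.
- Not replaced: 0.0467 × 0.9125 + 0.1866 × 0.7064 = 0.174; given the first step, 0.174 / 0.233 = 0.75.

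At p = 1/3:

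- P(X = 0) = 0.0878 and P(X = 1) = 0.2634, so the first step is passed with probability 0.351.
- Replaced: 0.0878 × 0.8999 + 0.2634 × 0.6804 = 0.258; given the first step, 0.735.
- Not replaced: 0.0878 × 0.9529 + 0.2634 × 0.8033 = 0.295; given the first step, 0.841.

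| Assumed true DLT rate | Both steps: replaced | Both steps: not replaced | Given first step: replaced | Given first step: not replaced |
|---|---|---|---|---|
| 1/3 | 0.258 | 0.295 | 0.735 | 0.841 |
| 40% | 0.140 | 0.174 | 0.600 | 0.748 |

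**Size if all 12 must be evaluable**

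6 / 0.8 = 7.5, so 8. Maximum 45 + 8 = 53; likely 23 + 8 = 31 to 29 + 8 = 37. Inflating 36 + 6 = 42 in one step agrees: 42 / 0.8 = 52.5, so 53.

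**The case against.** The strongest reply is that Section 13.6.1 already settles the matter. It replaces patients who are inevaluable for any reason, and Table 3 leaves out the word evaluable for the escalation cohorts too, where evaluability plainly applies. This stands in part: applied to the expansion, the denominator is 12 evaluable and the bias disappears. It does not explain why Section 13.2 budgets for inevaluability in one part of the trial and not the other, or why footnote B names an evaluable number of 6 and then switches to 12 treated.

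A reader might infer three stronger things, none of which the documents support.

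- That the rule is settled as 12 treated patients, so a too-toxic dose will be confirmed. Section 13.6.1 contradicts this; the wording is in conflict, not decided.
- That the rule typically means 3 DLTs in 9 or 10 patients, with the chance of confirming rising from 0.39 to 0.60 at a true rate of 1/3, or from 0.23 to 0.43 at 40%. Those figures expose all 12 patients to inevaluability, against the floor of 6 in footnote B, and leave out the earlier step of at most 1 DLT in 6.
- That the 3 DLTs might be counted over the 6 added patients only. The Table 3 column header counts DLTs at a given dose level and the sub-header speaks of a total of 12, so this reading is weak.

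Two further points are fair. The escalation maximum of 36 is six levels of 6, while the longest path through Table 2 visits five (for example 1, 2, 3A, 4A, 4B), so 30 evaluable and 30 / 0.8 = 37.5, or 38. On that count 38 + 8 = 46 is within 51, leaving aside a failed expansion; 53 therefore holds only on the plan's own figure of 36. Also, Section 6.7.4 allows an RP2D below the MTD on overall tolerability, so the DLT count is not the only safeguard.

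**Conclusion.** The passages conflict on the denominator of the rule that confirms the MTD, and the sample size follows the less protective side. Without replacement in the expansion, the chance of taking a dose through both steps rises by about 3 to 4 percentage points at true DLT rates of 40% and 1/3. For a dose that has already reached expansion, the rise is about 15 points at 40% and 11 points at 1/3. With replacement there is no bias, only an expansion figure that makes no provision for it.

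These sizes rest on assumed DLT rates, on the plan's upper figure of 20% inevaluable, and on inevaluability unrelated to DLT risk. A lower inevaluability rate gives a smaller effect in the same direction. This is a consistency fault in the primary decision rule that is worth correcting; it does not show that the trial will select too toxic a dose.

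**What to change.** - In Sections 3.1 and 13.1 and in Table 3 (sub-header and footnote B), write 12 DLT-evaluable patients in place of 12 treated or enrolled.
- State that the replacement rule in Section 13.6.1 applies to the expansion, and that the count of at most 3 against at least 4 DLTs is taken over all 12 evaluable patients at that dose level.
- In Section 13.2, and where Section 3.1 repeats the figures, apply the 20% allowance to the 6 added patients and restate the size as 53, likely 31-37. Say that this uses the plan's escalation figure of 36 and does not cover a failed expansion.

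The cost is a few wording changes and up to about 2 more patients in the stated size, which Section 13.6.1 already implies.
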